## **8 SPONSOR PROTOCOL/SAFETY REPORTING**

### **8.1 SAFETY REPORTING CRITERIA TO THE PHARMACEUTICAL COLLABORATORS**

#### **8.1.1 General Information and Summary**

Merck is providing pembrolizumab for participants in this clinical trial. As part of the agreement, information about the trial, including adverse events will be shared with them.

Unless otherwise agreed to with Merck, Merck-provided/-specific forms will be used to report events to Merck during the course of this study. These will be provided to the Principal Investigator and study team, and maintained in the regulatory files.

#### **8.1.2 Reporting Timeframes/Requirements**

For the purposes of reporting:

- From the time that the consent form is signed but before initiation of treatment:
  - All adverse events that occur must be reported if they cause the subject to be excluded from the trial, or are the result of a protocol-specified intervention, including but not limited to washout or discontinuation of usual therapy, diet, or a procedure.
  - Any serious adverse event, or follow up to a serious adverse event, including death due to any cause other than progression of the cancer under study that occurs to any subject must be reported within 2 working days to Merck Global Safety if it causes the subject to be excluded from the trial, or is the result of a protocol-specified intervention, including but not limited to washout or discontinuation of usual therapy, diet, or a procedure.

**NOTE:** These same reporting requirements and windows apply to Events of Clinical Interest (see Section **8.1.4**).

- From the time after treatment allocation through 90 days following cessation of treatment, or 30 days following cessation of treatment if the subject initiates new anticancer therapy, whichever is earlier:
  - Any serious adverse event, or follow up to a serious adverse event, including death due to any cause other than progression of the cancer under study, whether or not related to the Merck product, must be reported within 2 working days to Merck Global Safety.
  - Additionally, any serious adverse event, considered by an investigator who is a qualified physician to be related to Merck product that is brought to the attention of the investigator at any time following consent through the end of the specified safety follow-up period specified in the paragraph above, or at any time outside of

the time period specified in the previous paragraph also must be reported immediately to Merck Global Safety.

**NOTE:** These same reporting requirements and windows apply to Events of Clinical Interest (see Section [8.1.4](#)).

All patients with serious adverse events must be followed up for outcome.

**SAE reports and any other relevant safety information are to be forwarded to the Merck Global Safety [contact].** See [APPENDIX B](#) for the specific criteria and categories of information that require documentation and reporting to Merck with each event.

### 8.1.3 Serious Adverse Events

In addition to the serious adverse events listed in Section [7.1.1](#), the following are also required to be reported as “serious” events to Merck:

- Is a new cancer (that is not a condition of the study)
- Is associated with an overdose (see additional information in Section [8.1.4.1](#))

### 8.1.4 Reporting Requirements for Events of Clinical Interest

Selected non-serious and serious adverse events are also known as Events of Clinical Interest (ECI) and must be reported within 2 working days to Merck Global Safety. (Attn: Worldwide Product Safety; [contact]).

All ECI reporting time frames are indicated above in Section [8.1.2](#).

#### 8.1.4.1 Overdose of a Merck Product

For purposes of this trial, an overdose of pembrolizumab will be defined as any dose of 1,000 mg or greater ( $\geq 5$  times the indicated dose) and is a reportable event of special interest. No specific information is available on the treatment of overdose of pembrolizumab. Appropriate supportive treatment should be provided if clinically indicated. In the event of overdose, the subject should be observed closely for signs of toxicity. Appropriate supportive treatment should be provided if clinically indicated.

If an adverse event(s) is associated with (“results from”) the overdose of a Merck product, the adverse event(s) is reported as a serious adverse event, even if no other seriousness criteria are met.

If a dose of Merck’s product meeting the protocol definition of overdose is taken without any associated clinical symptoms or abnormal laboratory results, the overdose is reported as a non-serious Event of Clinical Interest (ECI), using the terminology “accidental or intentional overdose without adverse effect.”

#### 8.1.4.2 Liver Function Tests (LFTs)

An elevated AST or ALT lab value that is greater than or equal to 3X the upper limit of normal and an elevated total bilirubin lab value that is greater than or equal to 2X the upper limit of normal and, at the same time, an alkaline phosphatase lab value that is less than 2X the upper limit of normal, as determined by way of protocol-specified laboratory testing or unscheduled laboratory testing, are also to be reported as events of clinical interest to Merck in an expedited fashion.

**NOTE:** These criteria are based upon available regulatory guidance documents. The purpose of the criteria is to specify a threshold of abnormal hepatic tests that may require an additional evaluation for an underlying etiology.

#### 8.1.4.3 Reporting of Pregnancy and Lactation to Merck

Although pregnancy and lactation are not considered adverse events, it is the responsibility of investigators or their designees to report any pregnancy or lactation in a subject (spontaneously reported to them) that occurs during the trial.

Pregnancies and lactations that occur from the time of treatment allocation through 120 days following cessation of pembrolizumab, or 30 days following cessation of treatment if the subject initiates new anticancer therapy, whichever is earlier, must be reported by the investigator. All reported pregnancies must be followed to the completion/termination of the pregnancy. Pregnancy outcomes of spontaneous abortion, missed abortion, benign hydatidiform mole, blighted ovum, fetal death, intrauterine death, miscarriage and stillbirth must be reported as serious events (Important Medical Events). If the pregnancy continues to term, the outcome (health of infant) must also be reported.

Such events must be reported within 2 working days to Merck Global Safety. (Attn: Worldwide Product Safety; [contact])

#### 8.1.5 Protocol-Specific Exceptions to Serious Adverse Event Reporting

Efficacy endpoints as outlined in this section will not be reported to Merck as described in Section **8.1.2**, unless there is evidence suggesting a causal relationship between the drug and the event. Any such event will be submitted to Merck Global Safety within 2 working days either by electronic or paper media.

Specifically, the suspected/actual events covered in this exception include any event that is disease progression of the cancer under study.

The PI will monitor unblinded aggregated efficacy endpoint events and safety data to ensure the safety of the patients in the trial. Any suspected endpoint which upon review is not progression of the cancer under study will be forwarded to Merck Global Safety as a SAE within 2 working days of determination that the event is not progression of the cancer under study.

In addition, hospitalization related to convenience (e.g., transportation issues etc.) will not be considered a SAE or a Protocol Deviation.

## 9 STATISTICAL CONSIDERATIONS

### 9.1 STATISTICAL HYPOTHESIS

- Primary Endpoint:
  - Overall response rate (ORR); this will be assessed at up to 24 months.
- Secondary Endpoints:
  - Type, grade, and frequency of toxicities
  - Duration of response
  - Progression-free survival (PFS)
  - Event-free survival (EFS)
  - Overall survival (OS)

**NOTE:** Each of the above will be assessed definitively when 24 months have passed since the last patient has been enrolled.

## **9.2 SAMPLE SIZE DETERMINATION**

The trial will be conducted in two cohorts using a single stage design for evaluating efficacy in each cohort since modestly high clinical response rates are expected in both cohorts.

In the GZL cohort, results from a prior study indicate that 3 of 3 patients had a complete response when treated with (authors data, manuscript accepted for publication). With 20 evaluable patients, there would be 91% power to rule out 50% and be consistent with 80% who may be able to experience a clinical response, using an exact binomial test with a 0.10 one-sided significance level. As an illustration, if 20 evaluable patients are enrolled, 14 of 20 (70.0%) who experience a clinical response would have an associated one-sided lower 90% confidence interval bound of 53.3%, and simultaneously an associated one-sided upper 90% confidence interval bound of 83.4%. This demonstrates that 14 responses in 20 patients would be a desirable result based on the parameters selected.

In the PCNSL and extranodal DLBCL cohort, newly published results in 5 patients suggest the overall response rate will be moderately high. With 20 evaluable patients, there would be 88% power to rule out 40% and be consistent with 70% who may be able to experience a clinical response, using an exact binomial test with a 0.10 one-sided significance level. As an illustration, if 20 evaluable patients are enrolled, 12 of 20 (60.0%) who experience a clinical response would have an associated one-sided lower 90% confidence interval bound of 43.3%, and simultaneously an associated one-sided upper 90% confidence interval bound of 75.1%. This demonstrates that 12 responses in 20 patients would be a desirable result based on the parameters selected.

Within the PCNSL and extranodal DLBCL cohort, the goal will be to enroll a total of 10 PCNSL patients and 10 extranodal DLBCL patients. By doing so, at the conclusion of the trial, there will potentially be adequate patients to make an approximate estimate of the response rate for each group, which could provide information that may guide future development in these patient subsets. While 20 patients may be needed for evaluation per cohort, in order to allow for a small number of inevaluable patients, we intend to initiate treatment in 48 eligible subjects. In order to also account for ineligible patients (i.e., screen failures who do not initiate treatment), the accrual ceiling will be set at 52 patients. If 18-20 patients may be accrued onto this trial per year, accrual should be completed within 2 to 2.5 years.

## **9.3 POPULATIONS FOR ANALYSES**

All patients who receive at least 2 doses of pembrolizumab, and who have both a baseline and follow-up scan at the appropriate time to assess response will be considered evaluable and included in the analyses.

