#### 3.2 DRUG ADMINISTRATION

Each cycle of treatment is 21 days or 3 weeks. The minimum window between cycles due to scheduling or other administrative reasons is 18 days (i.e., 21 days -3 days).

All patients will receive single-agent pembrolizumab at a fixed dose of 200 milligrams (mg) administered via intravenous (IV) infusion every 21 days (3 weeks). Dosing of pembrolizumab is fixed; not based upon subject weight. Infusions may be done peripherally or via central venous access device, etc.

Pembrolizumab will be administered as a 30-minute infusion. Every effort should be made to target the infusion timing as close to 30 minutes as possible; however, a preferred window of -5/+10 minutes to account for variability of infusion pumps is permitted (i.e., anticipated infusion window of 25-40 minutes).

Treatment will be on an outpatient basis; however, at the investigator's discretion (e.g., for additional monitoring, patient social reasons, etc.), patients may be treated on an inpatient basis. Any cases of planned hospitalization are not considered reportable serious adverse events per Section 7.

No premedications are required; however, may be used in specific patients at treating investigator discretion or as directed per toxicity management.

**NOTE:** The FDA-approved labeling contains additional specific instructions for the preparation of pembrolizumab infusion fluid and administration of infusion solution.

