#### 3.4.3 Imaging Studies

**NOTE:** Results from NIH only. These are done at the following time points during treatment (see Study Calendar for windows): after cycles 2 and 6, and months 9, 12, 18, and every 6 months thereafter during treatment.

- CT chest, abdomen and pelvis; and/or MRI of brain (in patients with PCNSL or those with known or suspected involvement of CNS)

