### 3.8 STUDY CALENDAR

Procedure	Screening	Baseline	Treatment Cycles				Disease Evaluations	End of Treatment	Post-Treatment Follow-Up		
			1	2	3+ odd	4+ even			Safety	Follow-Up (Prior to PD)	Survival (Post-PD)
Scheduling Window (Days):	-28 to -1 	-14 	-3	-3	-3	-3	During-Treatment 	Treatment discon./PD 	30-90 days 	Every 3, 6, or 12 months 	Every 3 months 
Physical Exam (including, history, vitals, weight, and height [screening only]); ECOG/Lansky PS	X	X	X	X	X	X		X		X	
Confirmation of Diagnosis	X										
CBC with Differential	X	X	X	X	X	X		X		X	
Chemistry Panels (i.e., Acute care and Hepatic)	X	X	X	X	X	X		X		X	
Mineral Panel, LDH, Uric Acid, Total Protein		X	X	X	X	X		X		X	
PT/INR and aPTT		X	X								
Thyroid Function (i.e., TSH, T3, T4)	X	X	X		X			X		X	
Urinalysis		X			X						
Pregnancy Test (urine/serum; WOCBP)	X	X	X								
Hepatitis B and C Testing	X										
HIV Antibody Testing		X									
TBNK and Quant. IG Panel		X			X			X		X	
Anti-Nuclear Antibody (ANA)		X									
Tumor Imaging: CT Scans, Brain MRI 	X	X					X	X		X	
 F-FDG-PET/CT Scan		X						X (PD) 			
Peripheral Blood Flow Cytometry 		X									
Bone Marrow Aspiration/Biopsy 		X									
Lumbar Puncture 		X						X			X
Ophthalmologic Evaluation (PCNSL patients) 	X	X	X								
Symptoms/Adverse Events Assessment, Concomitant Medication Review	X	X	X ..... X					X	X		
Research Tissues (archival/fresh biopsy) 		X		X				X (PD)			
Research Bloods, Saliva/Buccal, CSF Samples 		X	X	X		X(C6)	X	X			
Survival Status											X

**NOTE:** Additional assessments may be done as clinically indicated.

 Screening and Baseline evaluations should be performed within 28 days prior to enrollment and dosing, respectively, with the following exceptions: Confirmation of diagnosis (no time limit); HIV antibody, Hepatitis B surface antigen and Hepatitis C antibody (within 3 months). **NOTE:** Any screening tests performed within the specified time frame for baseline do not need to be repeated.

 Within 14 days prior to dosing on C1D1, with the following exceptions: Pregnancy test (within 72 hours of dosing; must be negative).

 To be done after cycles 2 and 6, and months 9, 12, 18, and every 6 months during treatment; or, as otherwise clinically indicated.

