 To be done within 30 days (+7 days) after treatment discontinuation (i.e., may coincide with the safety follow-up visit). If treatment is discontinued for a reason other than disease progression, assessments should be repeated at the time of progression. If subject to initiate new anti-cancer therapy assessments should occur before the first dose of the new therapy.

 Serious adverse events (SAEs) that occur within 90 days of the last dose of treatment and before initiation of new anti-cancer treatment must also be followed and recorded (see Section [3.7.1](#)).

 Follow-up to occur about every 3 months (+/- 2 weeks) for first 12 months, every 6 months for years 2-5 (+/- 4 weeks), and then annually (+/- 6 weeks) until disease progression or initiation of new anti-cancer therapy. See Sections [3.7.2](#) and [3.7.3](#) for special procedures on imaging.

 After disease progression or initiation of new anti-cancer therapy, contact for survival about every 3 months (+/- 4 weeks). See Section [3.7](#).

 CT scans (preferred) of chest, abdomen and pelvis at baseline; may be adjusted to assess known sites of disease, as needed (e.g., other sites of disease and/or other modalities such as MRI). MRI of brain (required in patients with PCNSL at baseline); as clinically indicated in other patients at baseline and as clinically indicated in follow-up. Scans performed after cycles 2 and 6, at 9, 12, 18 months and every 6 months thereafter during treatment.

 F-FDG PET/CT (at disease progression if clinically indicated)

 Peripheral blood flow cytometry for diagnostic and staging purposes; repeat in follow-up to confirm response or progression, or as clinically indicated.

 Bone marrow aspiration/biopsy (within 3 months prior to starting treatment) if clinically indicated; repeat in follow-up to confirm response or progression.

 LP for cytology and flow cytometry required within 3 months prior to start of study therapy in patients with PCNSL and as clinically indicated in other patients; repeat in follow-up to confirm response or progression.

 Ophthalmologic evaluation required at baseline in patients with PCNSL; repeat in follow-up to confirm response or progression.

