#### **3.10.1 Criteria for Removal from Protocol Therapy**

- Completed 24 months or more of uninterrupted treatment with pembrolizumab without disease progression per Section [3.5.2.1](#) at the discretion of the treating investigator/subject. **NOTE:** Patients may be eligible for up to one year of additional study treatment if they progress after stopping study treatment provided they meet the requirements detailed in Section [3.5.3](#).
- Achieved a complete response (CR) and completed at least 1 year of treatment with pembrolizumab per Section [3.5.2.2](#) at the discretion of the treating investigator/subject. **NOTE:** Patients may be eligible for up to one year of additional study treatment if they progress after stopping study treatment provided they meet the requirements detailed in Section [3.5.3](#).
- Confirmed radiographic disease progression
  - A subject may be granted an exception to continue on treatment with confirmed radiographic progression if clinically stable or clinically improved, please see Section [3.5.1](#).
- Unacceptable toxicity as listed in Section [3.3.2](#).
- Intercurrent illness that prevents further administration of treatment
- Requirement for use of prohibited therapies as listed in Section [4.2](#)
- Pregnancy
- Subject's requests to be withdrawn from protocol therapy
- Noncompliance with trial treatment or procedure requirements
- Investigator's decision to withdraw the subject
- Study is cancelled for any reason

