### 6.3.7 Other

Evaluable for toxicity: All patients who receive at least 1 dose of pembrolizumab will be evaluable for toxicity.

**Evaluable for objective response:** Only those patients who have measurable or evaluable disease present at baseline, have received at least two doses of therapy, and have had their disease re-evaluated with radiographic imaging will be considered evaluable for response. These patients will have their response classified according to the definitions stated below. (NOTE: Patients who exhibit objective disease progression prior to the end of cycle 1 will also be considered evaluable.)

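### The only efficacy set (two doses plus a follow-up scan) omits the cycle-1 progression note and has no non-responder rule, so ORR is biased upward if excluded patients respond less often than those analysed

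*Combined protocol and SAP*

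**What the plan says.** Section 9.3 names one population for the efficacy analyses: "All patients who receive at least 2 doses of pembrolizumab, and who have both a baseline and follow-up scan at the appropriate time".

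Section 6.3.7 defines who is evaluable for objective response. These patients must have measurable or evaluable disease at baseline, "have received at least two doses of therapy, and have had their disease re-evaluated with radiographic imaging". It then adds a note: "Patients who exhibit objective disease progression prior to the end of cycle 1 will also be considered evaluable". Section 9.3 does not repeat the note. Section 6.3.7 also has a set of patients with at least one dose, but for toxicity only.

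On timing, section 3.2 says "Each cycle of treatment is 21 days or 3 weeks", and section 3.4.3 places on-treatment imaging "after cycles 2 and 6, and months 9, 12, 18, and every 6 months thereafter during treatment". Two other routes to a scan appear in the Study Calendar (section 3.8). Footnote 3 allows disease evaluation "every 6 months during treatment; or, as otherwise clinically indicated". Tumor imaging is also marked at end of treatment, with footnote 4 reading "To be done within 30 days (+7 days) after treatment discontinuation".

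Section 9.2 bases power on 20 evaluable patients per cohort and plans to treat 48 to allow for a few who are not evaluable. Section 9.4.2 reports the ORR per cohort with a 95% confidence interval. No all-treated analysis is planned.

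**The concern.** The denominator depends on what happens after treatment starts. To be counted, a patient must receive a second dose and reach a scan. In relapsed or refractory aggressive lymphoma, some who do neither will be early failures, and the plan removes them instead of scoring them as non-responders.

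The two sections also disagree. A patient with scan-proven progression in cycle 1 after one dose is a non-responder under 6.3.7 and absent under 9.3.

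At stake are the primary estimate and its interval, and any statement that 50% (GZL) or 40% (extranodal DLBCL) has been ruled out for the patients who were treated.

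**Working it through.** **Inputs.** From section 9.2: 20 evaluable per cohort; null and target rates of 50% and 80% (GZL) and 40% and 70% (extranodal DLBCL); exact binomial test at one-sided 0.10; 48 to be treated. Assumed here: an even split, which gives up to (48 − 40)/2 = 4 exclusions per cohort.

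**The plan's own figures.** The smallest passing counts are 14/20 (exact size 0.0577, power 0.913) and 12/20 (size 0.0565, power 0.887). One response fewer gives 0.132 and 0.128, above 0.10. The one-sided 90% bounds are 53.3% and 83.4% for 14/20, and 43.3% and 75.1% for 12/20. All agree with 9.2 (stated power 91% and 88%).

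**Who falls outside the set.** Two 21-day cycles put the first planned scan at about day 42. The 6.3.7 note reaches only to about day 21. Even with the note, a patient who dies, is lost or stops without a scan before day 42 is left out.

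**Effect on the chance of passing.** Let the all-treated ORR equal the null p0, with m patients excluded, r of them responders, and 20 analysed. The ORR among those analysed is

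p_E = (p0 × (20 + m) − r) / 20.

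For GZL with m = 2 and r = 0, this is 0.50 × 22/20 = 0.55. With r = 0 throughout:

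| Excluded, all non-responders | GZL p_E | P(≥14/20) | Extranodal p_E | P(≥12/20) |
|---|---|---|---|---|
| 0 | 50.0% | 0.058 | 40.0% | 0.057 |
| 1 | 52.5% | 0.088 | 42.0% | 0.081 |
| 2 | 55.0% | 0.130 | 44.0% | 0.112 |
| 3 | 57.5% | 0.184 | 46.0% | 0.151 |
| 4 | 60.0% | 0.250 | 48.0% | 0.198 |

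**Milder cases, four excluded.**
- One responder: p_E = (12 − 1)/20 = 55% and (9.6 − 1)/20 = 43%; chances 0.130 and 0.096.
- Two responders: p_E = 50% and 38%; chances 0.058 and 0.038. There is no inflation, and the extranodal ORR is biased slightly downward.

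**Break-even.** The 0.10 level is exceeded only if the excluded patients' ORR is below about 17% (GZL) or 7% (extranodal) with two exclusions, or 34% or 24% with four. With one exclusion it is never exceeded.

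**Same counts, all-treated denominator.** One-sided 90% lower bounds:
- 14 responders: 53.3% of 20, 50.3% of 21, 47.7% of 22, 43.3% of 24.
- 12 responders: 43.3% of 20, just under 41% of 21, 38.9% of 22, 35.3% of 24.

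One excluded non-responder leaves the conclusion standing in each cohort. Two overturn it.

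**The case against.** **The plan's test is not wrong on its own terms.** Section 9.2 frames the nulls and power on evaluable patients, and for that rate the test keeps its size (0.058 and 0.057). A reader might infer that the type I error is miscalculated. It is not. Inflation appears only when the result is read as applying to all treated patients. This stands.

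**The gap is narrower than 9.3 alone suggests.** A reader might infer that every early progressor is dropped. Section 6.3.7 keeps objective progression in cycle 1, and 9.3 is silent on that note without contradicting it. End-of-treatment and clinically indicated scans can keep two-dose patients in. Objective progression after cycle 1 in a patient with only one dose requires a missed or delayed second dose. What remains is early death, loss or stopping without a scan, and one-dose patients without cycle-1 progression. Section 9.3 also does not say whether unscheduled scans meet its timing condition.

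**Exclusion is not the same as failure.** Section 3.10.1 also lists unacceptable toxicity, patient request and "Intercurrent illness that prevents further administration of treatment" as reasons to stop. It is not enough that some excluded patients fail; they must respond less often than those analysed.

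**Size.** Four per cohort uses the whole allowance, although 9.2 expects few. The set-up matters too: fixing 24 treated, so that p_E = p0 × 24/(24 − m), gives about 0.12 and 0.11 with two exclusions. Section 11.2 records a decision to close accrual early, so 20 evaluable may not have been reached. Section 9.4.2 reports an interval and states no success rule.

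**Time-to-event endpoints.** A reader might infer that early events are also removed from PFS, EFS and OS, since 9.4.3 names no population. Sections 6.3.5 and 6.3.6 start PFS and EFS at enrollment and count death as an event, which points the other way.

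**Conclusion.** The point holds as a conditional bias in the primary ORR, together with an inconsistency between 9.3 and 6.3.7. The text is clear: there is one efficacy set, without the cycle-1 note, and no rule scoring unassessed treated patients as non-responders. ORR is too high if excluded patients respond less often than those analysed.

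The tabulated probabilities are worst cases. They assume 20 evaluable per cohort, an all-treated ORR at the null and no responders among the excluded. On those assumptions the nominal 0.10 survives one exclusion and is exceeded from two.

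The documents do not support saying that the ORR is biased by a known amount or that the planned set must be discarded. For PFS, EFS and OS, naming all treated patients would be a clarification only. This should be fixed; confidence is high on the text and limited on the size.

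**What to change.** 1. Reconcile 9.3 with 6.3.7 so that objective progression before the end of cycle 1 counts as non-response. State that end-of-treatment and clinically indicated scans count as follow-up scans.
2. Keep the planned evaluable-set ORR. Beside it, report ORR with an exact 95% CI in all patients with at least one dose, with no further eligibility filter, counting those without a post-baseline assessment as non-responders. Declare it as added after the decision to close accrual. Claim that 50% or 40% is ruled out only if the all-treated result agrees at the actual treated n. At one-sided 0.10 the counts needed would be, for example, 14 (GZL) and 12 (extranodal) of 21, 15 and 13 of 22, or 16 and 14 of 24.
3. Tabulate the number of treated patients outside the evaluable set and the reason for each.
4. As a clarification, state that PFS, EFS and OS use all treated patients.

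**Cost.** Wording and one extra table, from data already collected. Replacing the primary set this late in an open-label study would be debatable; adding an estimate and labelling it as late is not.

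The all-treated ORR may be lower. If the 80% and 70% targets hold in all treated patients, power is 0.94/0.91 at n = 22 and 0.96/0.93 at n = 24. If they hold only in the 20 evaluable, two non-evaluable failures mean that 15 or 13 responses must come from those 20, and power falls from 0.91/0.89 to 0.80/0.77. With four (16 or 14 needed) it falls to 0.63/0.61.
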